#### **4.5 Subject Lost to Follow-up**

A subject will be considered lost to follow-up if they fail to attend a scheduled visit (including the safety follow-up visit) and is unable to be contacted by the study site.

Every reasonable effort should be made to contact the subject and will include a minimum of three documented phone calls (each performed at different times of the day) and, if necessary, a certified letter to the subject's last known mailing address or local equivalent methods. All contact attempts are to be documented in the source documents.

#### **4.6 Prior and Concomitant Therapy**

All medications used up through the safety follow-up visit are to be recorded.

##### **4.6.1 Prior Medication**

Prior medication is defined as any medication taken before the date of the first dose of study drug.

##### **4.6.2.1 Permitted, Restricted, and Prohibited Medications**

Prohibitions and restrictions for concomitant medications should be followed between the initial Baseline visit and Visit 9/ET as specified in [Appendix A](#) and [Appendix B](#). These appendices do not constitute an exhaustive list and any questions regarding prohibited and restricted medications should be discussed with the Medical Monitor or designee.

Use of medications that could interfere with study conduct or any questions regarding prohibited and restricted concomitant medications should be reviewed and/or discussed with the Medical Monitor or designee.

Medications that can prolong QT interval are prohibited (or restricted if approved by the Medical Monitor) as specified in Appendix A.

Permitted concomitant medications should remain at a stable dose throughout the study.

If a subject is on a medication restricted by the protocol, the medication should be adjusted if it is determined by the Investigator to be clinically appropriate (e.g., if the subject's

symptoms are not well-controlled or if the subject cannot tolerate the current medication) in consultation with the treating physician.

Subjects who require current treatment with a prohibited medication will be withdrawn from the study.

Subjects who have previously taken a prohibited medication during the study will be withdrawn from the study unless:

- the prohibited medication has been discontinued AND
- withdrawal from the study presents an unacceptable medical risk to the subject

The justification to allow the subject who has taken a prohibited medication to continue in the trial will be made by the Sponsor/Medical Monitor, with medical input from the Investigator, and will be documented. If a subject is allowed to remain in the trial, this will be reported as a major protocol deviation and not a waiver.

## **5 INVESTIGATIONAL PRODUCT**

### **5.1 Investigational Product Description**

The investigational product will be pimavanserin 34 mg (provided as 2×17 mg tablets). Tablets will be administered orally as a single dose once daily.

#### **5.1.1 Formulation, Appearance, Packaging, and Labeling**

The Sponsor will supply pimavanserin 17 mg tablets.

Pimavanserin tartrate is a white to off-white powder. Pimavanserin 17 mg tablets include the active compound (pimavanserin tartrate) and the following excipients: pregelatinized starch, magnesium stearate, and microcrystalline cellulose, and the tablet coating is [REDACTED]. The drug product is formulated with standard pharmaceutical excipients at 17 mg strength (20 mg of pimavanserin tartrate).

Pimavanserin tablets are manufactured under current Good Manufacturing Practices.

During the treatment period, study drug will be distributed in a quantity sufficient to ensure the subject has an adequate supply of study drug between study visits. In addition to the study drug dispensed at the site, investigational product may be delivered to the subject's home.

#### **5.1.2 Product Storage and Stability**

Investigational product must be stored between 15°C and 30°C (59°F and 86°F) in a secure area with restricted access and according to local and national regulations.

### **5.1.3 Dosing and Administration**

Eligible subjects will begin pimavanserin once-daily dosing at 34 mg. Study drug will be dispensed to the subject to take home at the Baseline visit. The subject will be instructed to take the first dose of study drug on the day after the Baseline visit. It is recommended that the subject should take the study drug at approximately the same time each day.

Each daily dose consists of two individual tablets that should be taken together. Subjects should be instructed to take two whole tablets, orally, once daily. Subjects should be instructed to not crush the tablets. The tablets may be taken with or without food.

### **5.1.4 Method of Assigning Subjects to Treatment Groups**

All subjects will receive once daily doses of pimavanserin over 52 weeks of treatment. Details of pimavanserin dosing and administration are provided in Section 5.1.3.

### **5.1.5 Blinding**

This is an open-label study.

### **5.1.6 Study Drug Compliance**

If a subject misses one dose of study drug, he or she should not take an extra dose the next day. Subjects who are less than 80% compliant with study drug as assessed at more than one study visit should be discussed with the Medical Monitor or designee.

### **5.1.7 Overdose**

An overdose is a deliberate or inadvertent administration of a treatment at a dose higher than the maximum recommended dose per protocol. It must be reported, irrespective of outcome, even if toxic effects were not observed ([Section 7.4.4](#)). All events of overdose are to be captured as protocol deviations.

## **5.2 Investigational Product Accountability Procedures**

The used and unused treatment kits, blister cards, and tablets from Study ACP-103-054 and Study ACP-103-059 are to be collected by the Investigator as part of the EOT visit of Study ACP-103-054 and Study ACP-103-059 before study drug for the present study can be dispensed.

The Investigator or designee will keep current and accurate records of the study drug product dispensed, used, and returned for each subject to assure the regulatory authority and the Sponsor that the study drug is being handled appropriately. Subjects should be instructed to return all packaging and unused study drug to the Investigator at regularly scheduled clinic visits and ET visits. Unused study drug and packaging may also be returned to site staff when

visiting the subject's home. Any study drug supplied is for use in this study only and should not be used for any other purpose.

At appropriate intervals during the study, study drug reconciliation will be performed by the Sponsor (or designee) who may return appropriate unused study drug and used and unused packaging to the Sponsor's designee for destruction.

At the conclusion of the study, final study drug reconciliation will be conducted at the site. Final study drug accountability documentation will be maintained at both the site and at the Sponsor. Any remaining unused study drug and all used and unused packaging will be sent back to the Sponsor's designee for destruction, as allowed by country specific regulations. Documentation of study drug destruction will be recorded and maintained by both the Sponsor and the Sponsor's designee.

## **6 STUDY PROCEDURES**

Study specific procedures are detailed below. All assessments will be completed according to the schedule described in [Table S-1](#). Every effort should be made to complete the required procedures and evaluations at the designated visits and times.

### **6.1 Baseline Assessments**

Subject consent for the present study **must be** obtained prior to the final procedures being performed at the EOT visit of Study ACP-103-054 and Study ACP-103-059 and before any new procedures are performed for Study ACP-103-055. Data from the EOT procedures of Study ACP-103-054 and Study ACP-103-059 will be carried over to the ACP-103-055 study to be included as baseline information for the present study and this visit will be considered Baseline (Visit 1). Subject eligibility will be assessed by the site and the Sponsor through an eligibility review process.

#### **6.1.1 Medical History, Medication History, and Demographics**

Relevant information collected from Study ACP-103-054 and Study ACP-103-059 will be rolled over to the present study; any updates to this information should be collected during the Baseline visit of the present study. Any new medical condition beginning after the informed consent form (ICF) has been signed will be captured as an AE.

#### **6.1.2 Psychiatric History**

Relevant information collected from Study ACP-103-054 and Study ACP-103-059 will be rolled over to the present study; any updates to this information should be collected during the Baseline visit of the present study.

### **6.1.3 Background Antidepressant Adherence**

Review of subject adherence with background antidepressant therapy should be conducted at the Baseline visit and all visits.

## **6.2 Exploratory Efficacy Assessments**

### **6.2.1 Hamilton Depression Scale (17 Items)**

The HAMD-17 ([Hamilton 1960](#)) is completed with the Structured Interview Guide for the Hamilton Depression Rating Scale (SIGH-D) ([Williams 1988](#)) by the Investigator or designee based on an assessment of a patient's symptoms. The timeframe for this scale is the past 7 days. The HAMD-17 will be used for exploratory efficacy analyses and is to be the first scale completed at each visit.

### **6.2.2 Clinical Global Impression–Severity Scale**

The CGI-S ([Guy 1976](#)) is a scale used by the Investigator or designee to rate the severity of the disorder and the global improvement since beginning of the study. The CGI-S rates the severity of a patient's depression over the past 7 days and will be completed with a structured interview guide for global impressions (SIGGI) ([Targum et al. 2013](#)). The CGI-S will be performed at all scheduled visits and will be used for exploratory efficacy analyses.

### **6.2.3 Sheehan Disability Scale**

The SDS ([Sheehan et al. 1996](#)) is a three-item patient-facing questionnaire used to evaluate impairments in the domains of work, social life/leisure, and family life/home responsibility. All items are rated on an 11-point continuum (0=no impairment to 10=most severe). The timeframe for this scale is the past week. The SDS will be used for exploratory efficacy analyses.

### **6.2.4 Changes in Sexual Functioning Questionnaire Short Form**

Sexual functioning will be assessed using the CSFQ-14 ([Keller et al. 2006](#)), a 14-item version of the CSFQ ([Clayton et al. 1997](#)). This is a patient-facing questionnaire, with a male version and a female version, that provides scores for three scales corresponding to the phases of the sexual response cycle (i.e., desire, arousal, and orgasm) and the five scales of the original CSFQ (sexual desire, sexual frequency, sexual satisfaction, sexual arousal, and sexual completion). The CSFQ-14 will be used for exploratory efficacy analyses.

### **6.2.5 Karolinska Sleepiness Scale**

The KSS ([Akerstedt and Gillberg 1990](#)) is a patient-facing scale that measures the patient's drowsiness and is frequently used in studies measuring subjective sleepiness. Scoring is based on a 9-point verbally anchored scale ranging from "extremely alert" to "very sleepy,

great effort to keep awake, fighting sleep.” The timeframe for this scale is the past 7 days. The KSS will be used for exploratory efficacy analyses.

### **6.2.6 Impact of COVID-19 Pandemic on Exploratory Efficacy Assessments**

Subjects who cannot attend clinic visits due to the COVID-19 pandemic are allowed to participate in remote visits via telephone or video, or site staff can visit subjects in their homes.

## **6.3 Safety Assessments**

### **6.3.1 Physical Examinations**

A general physical examination will be conducted at Baseline and Weeks 28 and 52.

### **6.3.2 Vital Signs**

Vital signs will include body temperature, resting respiration rate, sitting systolic and diastolic blood pressure, and pulse rate. The sitting blood pressure should be measured after the subject has been sitting for  $\geq 3$  minutes.

Vital signs will be measured at all scheduled and unscheduled visits and will be used for exploratory safety analyses.

### **6.3.3 Weight and Body Mass Index**

Weight will be measured at all scheduled and unscheduled visits and will be used for exploratory safety analyses. The height recorded in Study ACP-103-054 or Study ACP-103-059 will be used.

Body mass index will be calculated using the following formula:

$$\text{Weight (kg)} / [\text{height (m)}]^2.$$

### **6.3.4 Electrocardiograms**

All 12-lead electrocardiograms (ECGs) will be complete, standardized recordings. A single 12-lead ECG will be completed at all scheduled visits at the investigator site during the present study (Table S-1). In the US and UK, a 6-lead ECG device will be given to subjects in order to perform ECGs on themselves at home when they cannot go the clinic and site staff cannot go to their home. This should be done in discussion with the Medical Monitor. When an ECG is performed outside of the investigator site, this should be documented in the source record. All ECGs will be centrally read; the interpretation by the central cardiologist is considered the official result. If a site performs additional ECGs beyond the single ECG prescribed at Baseline, the mean QTcF/QRS values of all the tracings of adequate quality will be used to determine eligibility.

At Baseline, a subject may be enrolled based on the machine read of the locally completed ECG. If the interpretation of the ECG by the central cardiologist returned after enrollment indicates QTcF outside of the allowable range, the subject will be discontinued from the study, but this will not be considered a protocol deviation.

Electrocardiograms should be performed before blood sampling or at least 30 minutes after blood sampling. The subject must rest in a supine position for 5 minutes before the ECG is obtained. ECG tracings (paper or electronic) will be reviewed and interpreted by a qualified clinician. ECG tracings and results (ventricular rate, PR, QRS, QT, QTcF and QTcB intervals) will be included and summarized in the subject's study records.

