Phase 3 PDP program with a clinical dose of 34 mg. An average prolongation of approximately 5-8 ms was observed. No clinically significant patterns have been observed in serious adverse events (SAEs) and there has been no evidence of pimavanserin-related laboratory abnormalities.

Always refer to the latest version of the pimavanserin Investigator’s brochure for the overall benefit/risk assessment and the most accurate and current information regarding drug metabolism, pharmacokinetics, efficacy, and safety.

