5.3.1 Unscheduled Assessments

Both scheduled and unscheduled assessments, including early termination visits and remote visits, will be considered for planned timepoint summaries. All assessments will be presented in data listings.

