14.2 Clinical Laboratory Variables

Clinical laboratory tests are performed at Baseline, Week 12, and Week 52 (EOT/ET).

In general, laboratory test results are from a central laboratory. Due to COVID-19 disruptions it is possible that some test results may be collected from a local laboratory. A separate eCRF will capture local laboratory results in order to facilitate medical monitoring of subject safety. Local laboratory results will not be included in any summary data analysis; they will, however, be included in separate data listings. All results (central and local) will be displayed in Système International [SI] units. It is encouraged, but not required, that clinical labs be completed under fasting conditions. The listings will include date and study day of collection. Out of range values will be flagged in the data listings.

- Hematology tests
 - Complete blood count (CBC) including:
 - White blood cell (WBC) count
 - Complete differential (relative and absolute)
 - Hematocrit (Hct), hemoglobin (Hgb), red blood cells (RBC), platelets
 - Reticulocyte count
- Clinical chemistry serum tests
 - Sodium (Na), potassium (K), chloride (Cl), phosphorus (P), calcium (Ca), carbon dioxide (CO₂), blood urea nitrogen (BUN), creatinine (Cr), uric acid
 - Alanine aminotransferase (ALT), aspartate aminotransferase (AST), gamma-glutamyl transpeptidase (GGT), alkaline phosphatase (ALP), total bilirubin (TBIL), lactate dehydrogenase (LDH)
 - Glucose
 - Albumin (ALB), total protein
 - Prolactin
 - Creatine kinase (CK)/creatinine phosphokinase (CPK)
 - Lipid panel
 - Total cholesterol, high-density lipoprotein (HDL)-cholesterol, triglycerides, low-density lipoprotein(LDL)-cholesterol, very low density lipoprotein cholesterol
- Urinalysis
 - Blood, RBCs, WBCs, protein, glucose, ketones, specific gravity, pH

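### Home 6-lead ECGs enter the QTcF changes, maxima and outlier counts together with clinic 12-lead ECGs, and the SAP states no distinction by device

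*Protocol*

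**What the plan says.** The standard recording is defined in Protocol 6.3.4: "A single 12-lead ECG will be completed at all scheduled visits at the investigator site during the present study". The same section adds that in the US and UK "a 6-lead ECG device will be given to subjects in order to perform ECGs on themselves at home". This applies only when the subject cannot reach the clinic and staff cannot visit, and it is to be discussed with the Medical Monitor. Reading is central for every tracing: "All ECGs will be centrally read; the interpretation by the central cardiologist is considered the official result". For recordings made elsewhere, "When an ECG is performed outside of the investigator site, this should be documented in the source record".

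On analysis, SAP 5.3.1 states: "Both scheduled and unscheduled assessments, including early termination visits and remote visits, will be considered for planned timepoint summaries". SAP 5.3.2 says that extreme-value summaries, such as the post-baseline maximum and overall PCI counts, draw on every non-missing value after Baseline, whether or not it was chosen for the by-visit table. SAP 14.4 summarizes QTcF values and changes by visit, puts them in categories by visit and at the overall maximum, and counts PCI values (above 500 ms, or a change above 60 ms). It does not refer to lead number, device or place of recording. The ECG footnote to the schedule in SAP Appendix A describes only the 12-lead recording; the matching footnote to Protocol Table S-1 also describes the 6-lead device.

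**The concern.** QT prolongation is a documented effect of this drug. Protocol 1.3 reports: "An average prolongation of approximately 5-8 ms was observed". Baseline is the end-of-treatment visit of the antecedent study, scheduled as a clinic visit with a 12-lead ECG. A later home tracing therefore normally gives a 6-lead value minus a 12-lead value, and the tables treat that difference like any other change. If the two devices differ systematically, the mean change moves. If the self-recorded tracing is merely noisier, the mean is unaffected on average, but the largest of several values per subject tends to rise, and the outlier counts rise with it. There is no concurrent control arm from which a device effect could be subtracted. A reader of the finished tables could not tell how many values came from the home device.

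**Working it through.** The plan has no figure of its own to reproduce. It gives no 6-lead minus 12-lead difference, no share of home ECGs and no SD for QTcF change. All of these are assumptions below.

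**Step 1: do home tracings reach the tables?** Protocol 6.3.4 permits them and sends them to the central reader. SAP 5.3.1 admits remote visits to the timepoint summaries. SAP 5.3.2 admits all values after Baseline to the maxima and overall PCI counts. SAP 14.4 makes no exception. No sentence says outright that the two kinds are pooled; it follows from applying the general rules.

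**Step 2: shift in the mean change at a visit.** Let *f* be the share of ECGs at the visit that are 6-lead, *b* the mean 6-lead minus 12-lead difference, and *d* the true mean change from a 12-lead Baseline. Then

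(1 − f) × d + f × (d + b) = d + f × b,

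so the shift is f × b, upward or downward according to the sign of *b*.

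| Share f | b = 0 ms | b = 5 ms | b = 10 ms |
|---|---|---|---|
| 5% | 0 | 0.25 | 0.5 |
| 10% | 0 | 0.5 | 1.0 |
| 25% | 0 | 1.25 | 2.5 |
| 50% | 0 | 2.5 | 5.0 |

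**Step 3: offset needed to equal or cancel 5 to 8 ms.** This is b = 5/f to 8/f: 50 to 80 ms at a 10% share, 20 to 32 ms at 25%, and 10 to 16 ms at 50%.

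**Step 4: maxima.** A simulation of 200,000 subjects took a true change of 5 ms, an SD of change of 15 ms (each recording has SD 15/√2 = 10.6 ms), the eight scheduled post-Baseline ECGs, and a 25% chance that each is 6-lead. Extra 6-lead noise, where present, has SD 15 ms.

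| Scenario | Max change >30 ms | Max change >60 ms |
|---|---|---|
| 12-lead only | 21.2% | 0.1% |
| Offset +10 ms, no extra noise | 31.4% | 0.3% |
| Offset −10 ms, no extra noise | 18.2% | 0.1% |
| No offset, extra noise | 30.8% | 1.0% |
| Offset +10 ms, extra noise | 43.8% | 3.3% |

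The noise-only result depends on the assumptions. At a 10% share it is 25.3% and 0.4%. With four ECGs instead of eight, at 25%, the >30 ms figure goes from 13.9% to 19.7%. With an SD of 12 ms (eight ECGs, 25%) it goes from 9.8% to 21.9%, and with 18 ms from 32.0% to 39.4%. The direction is the same throughout. The percentages are illustrative, not forecasts. The >500 ms count was not simulated, because the documents give no distribution of absolute QTcF.

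**The case against.** The strongest reply is that the route is narrow and controlled. The device is confined to two countries, is used only when clinic and staff home visits have both failed, and involves the Medical Monitor. All tracings go to the central reader, and the five-minute supine rest applies to every ECG, not only those in clinic. This stands. It makes a high share of home ECGs less likely, although central reading removes differences between readers, not differences of lead set or self-recording.

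A second reply is that a device rule may exist elsewhere. SAP 5.3.2 refers to a separate programming conventions document, and SAP 3.6 to COVID-19 data guidance in the Data Management Plan. Neither is available, so the gap can be asserted only for the SAP text.

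Third, SAP 14.2 says of laboratory data, "Local laboratory results will not be included in any summary data analysis". That shows the SAP considered a pandemic change of source for one type of data, but it is not a true parallel: local laboratory results bypass the central laboratory, whereas home ECGs still reach the central reader. It does not prove inconsistent handling.

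Finally, the analyses are descriptive, nothing is tested, and ECG falls under other safety analyses in Protocol 9.5.3. That limits the consequence without removing it.

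**Conclusion.** The point holds as a low-priority improvement. Followed as written, the SAP mixes 6-lead and 12-lead values in the QTcF tables without distinguishing them. The mean change at a visit shifts by 0 to 5 ms if the offset is 0 to 10 ms and the share 5 to 50%. Both ranges are assumed, and zero is fully compatible with the documents. The outlier counts are the more exposed part, because noise alone, without any offset, can raise them.

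A reader might infer that the device change could pass for, or conceal, the known 5 to 8 ms drug effect. The documents do not support that. They give neither quantity needed to show it; at a 10% share it would take an implausible offset of 50 to 80 ms; and even the upper end of both assumed ranges together gives only 5 ms. The 5 to 8 ms figure also comes from a thorough QT study and the Parkinson's disease psychosis program. Subjects who received pimavanserin in the antecedent study have an on-drug Baseline in the main analysis, so a fresh change of that size is not expected in them. Concealment, if any, concerns mainly the means: noise pushes maxima up, and in the simulation a −10 ms offset lowered the >30 ms count only modestly.

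**What to change.** Carry a lead-type flag (12-lead or 6-lead) into the ECG analysis data. A flag for on-site or off-site would not do, because staff home visits are also off site. In SAP 14.4:

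- report the number of 6-lead ECGs at each visit;
- present the QTcF change, category and PCI tables for 12-lead ECGs alone, beside the all-ECG tables;
- mark 6-lead values in the PCI listing.

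Keeping both sets of tables loses no safety data. If the counts show few or no 6-lead tracings, the two sets will nearly coincide and the question is settled.

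The cost is one variable and a repeat of tables already planned. Two drawbacks remain. The 12-lead tables will have fewer values at remote visits. The flag may also take some retrieval: the protocol requires the source record to show only that an ECG was done off site, and the documents describe no case report form field for device, so lead type may have to come from the central ECG reader or from source.
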